6.2 DATA VALIDATION

Data validation (verification of case report forms against source data documents) is required for both prospective and retrospective studies in which data is being entered on case report forms. Validation should be completed by an independent, study monitor, internal or external to the investigator/sponsor institution, who is not involved in the conduct or oversight of the study. For database studies you will be required to attest that you have entered into a data use agreement with the database owner and that the data in the database has undergone validation/verification by that owner. A technical guide is available upon request to assist you in completing the following section.

The study team's certified clinical research professional (CCRP) will review all data fields on the data collections forms. Data validation will occur after patients complete their final assessment at 30-days. Charts will be reviewed in batches of five. A list of missing data or data fields that need to be updated will be created. All errors, if any, will be identified and corrected. When all variables are reviewed, the CCRP will review the action items with the study team. Corrected fields on the paper data collection form will be dated and initialed by the study team.

6.3 DATA / STATISTICAL ANALYSIS

All efficacy analyses will be intent to treat. The time to bowel function recovery and hospital length of stay will be compared between the two groups using Student's t-test. Due to the short-term nature of the outcome measures we expect no censoring.

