4.2 INCLUSION/EXCLUSION CRITERIA

4.2.1 *INCLUSION CRITERIA*

1. Subjects will be informed about the study, have read, understood, and signed the Informed Consent Form
2. Subjects of either gender that are ≥ 18 years of age
3. Subjects who can ambulate preoperatively
4. Subjects will have a Body-Mass Index (BMI) of $\leq 40\text{mg}/\text{m}^2$
5. Subjects with an ASA classification of 1, 2 or 3
6. Subjects not receiving an epidural to control perioperative pain
7. Subjects will be undergoing elective single-staged open ventral (incisional or midline) hernia repair
8. Subjects in which intra-operatively their surgical field/wound is characterized as Type 1 (Appendix II)
9. Subjects with a hernia defect $\geq 9\text{ cm}^2$ large

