4.2.2 EXCLUSION CRITERIA

1. Subjects who are not able to comprehend or comply with study requirements
2. Subjects who are pregnant
3. Subjects with BMI > 40
4. Subjects with autoimmune disorder requiring >10mg of a corticosteroid per day
5. Subjects with pre-existing systemic infections
6. Subjects with a wound-healing disorder
7. Subjects who have taken therapeutic doses of opioids for more than 7 consecutive days immediately prior to taking Alvimopan
8. Subjects who are immunocompromised such as HIV or transplant, or receiving chemo or radiation therapy
9. Subjects with a hernia defect < 9cm² large when measured intra-operatively
10. Subjects in which intra-operatively their surgical wound field/wound is characterized as Type 2, 3, or 4 (Appendix II)
11. Subjects in which the ventral incisional hernia repair requires more than one operation to reduce the hernia or to complete the hernia repair
12. Subjects with a hernia repair requiring an emergent procedure
13. Subjects in which untreated cancer was found intra-operatively
14. Subjects with cirrhosis or are currently being treated with dialysis
15. Subjects with severe hepatic impairment (Childs-Pugh class C)
16. Subjects with end-stage renal disease
17. Subjects scheduled for a concomitant procedure that involves the GI tract
18. Subjects with unplanned procedures that involve the GI tract
19. Subjects requiring post-operative NGT
20. Subjects participating in another prospective interventional study that involves the use of a device, drug, or surgery that would compromise the current study
21. Subjects with an epidural to control perioperative pain

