4.3.3 SAMPLE SIZE DETERMINATION

A total of 140 patients are expected to undergo research related treatments. The study will contain one open surgery arm. The open surgery arm will be a single-site prospective, randomized, double-blinded, placebo-controlled clinical trial with 1:1

randomization between the study drug and placebo with 70 patients in each group for a total of 140 patients in the study. An interim evaluation of efficacy will be conducted separately in the open surgery arm when half the patients have been recruited.

This study is expected to enroll up to 140 subjects from one academic medical center (Froedtert Hospital and the Medical College of Wisconsin) a site that performs state of the art hernia repairs and is a high volume hernia practices.

The study has been designed to provide at least 80% power to detect a 24-hour decrease in the time to return of bowel function in the treatment group compared to the control group at a one-sided 2.5% significance level. This corresponds to a two-sided 5% significance level, but acknowledges the one-sided nature of the study hypothesis. Based on data from studies of the experimental treatment in other contexts, as well as internal data, we expect a standard deviation of 48 hours. Adjusting for the increase in sample size to accommodate the planned interim analysis, 64 evaluable patients per group will provide the desired power. More details of the power characteristics are shown under the Interim Analysis section. We will recruit 70 patients in each arm to accommodate a 5-10% dropout rate.

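### The primary comparison is an unadjusted t-test; pre-specified adjustment for BMI, ASA class and hernia defect size could raise power at the same sample size if these variables are prognostic

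*Combined protocol and SAP*

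**What the plan says.** Section 6.3 is the whole analysis plan for efficacy: "The time to bowel function recovery and hospital length of stay will be compared between the two groups using" Student's t-test. It adds "All efficacy analyses will be intent to treat". It names no covariate or adjusted model, and section 4.4.2 names no stratification factor.

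Three patient characteristics have to be assessed for eligibility (sections 4.2.1 and 4.2.2):

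- BMI, with an upper limit of 40.
- ASA class: "Subjects with an ASA classification of 1, 2 or 3".
- Hernia defect area, with a floor of 9 cm² and no stated ceiling. The exclusion criterion refers to a defect below that floor "large when measured intra-operatively".

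Section 4.3.3 sizes the trial on the unadjusted comparison: "The study has been designed to provide at least 80% power to detect a 24-hour decrease in the time to return of bowel function", "at a one-sided 2.5% significance level. This corresponds to a two-sided 5% significance level", and "we expect a standard deviation of 48 hours". It requires 64 evaluable patients per arm and recruits 70. The table in section 6.1 gives overall power of 80.0% at the design effect.

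**The concern.** Whatever variation in recovery time these characteristics explain stays in the error term of a t-test. If they predict recovery, a model containing them estimates the arm effect with a smaller standard error and removes the effect of chance imbalance on them. The type I error is unaffected, provided the covariates are fixed in advance.

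The documents make a prognostic role plausible for defect size. Section 1 attributes prolonged ileus to bowel handling, opioids, inflammation and fluid shifts, which could reasonably grow with the extent of the repair. They do not say that they do.

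The power at stake matters because the design has little to spare. Stated power sits at the 80% target, and 10% dropout, the upper planned value, leaves 70 × 0.90 = 63 per arm, one short of the required 64. Adjustment is also much easier to defend if specified before the interim look than if added after an imbalance has been seen.

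**Working it through.** **Inputs from the documents.** Difference 24 h, SD 48 h, one-sided 2.5%, 64 evaluable per arm (section 4.3.3); one interim look at half information with third-degree power spending (section 6.1).

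**Assumed input.** R², the share of outcome variance explained jointly by the three covariates. The documents give no value, so 0 to 0.20 is shown.

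**Step 1: the plan's own power.**

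- Alpha spent at the interim: 0.025 × 0.5³ = 0.003125, so z = 2.734. Spending the remaining 0.021875 at the end gives a final boundary of z = 1.983 (nominal 0.0237).
- Drift: (24/48) × √(64/2) = 2.828.
- Interim power: 1 − Φ(2.734 − 2.828 × √0.5) = 1 − Φ(0.734) = 23.1%.
- Final look, by numerical integration: 57.2%. Overall: 80.4%.

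The plan states 22.9% + 57.1% = 80.0%, so its figure is reproduced to within half a point.

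**Step 2: gain before paying for the covariates.** Replace the SD by 48 × √(1 − R²), which is 46.8, 45.5 or 42.9 h at R² = 0.05, 0.10 or 0.20. Two-look power becomes 82.3%, 84.3% or 88.2%, against 80.4%.

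**Step 3: charge for estimating the covariates.** With k covariate terms, the error degrees of freedom are 2n − 2 − k. Chance imbalance multiplies the noncentrality by about √[(2n − 3 − k)/(2n − 3)]. With BMI, log defect area and ASA class as one ordinal term, k = 3, and at n = 64 the factor is √(122/125) = 0.988. The noncentral-t results below are for a single look at one-sided 2.5%, where the unadjusted t-test has 80.15% power.

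| Assumed R² | Noncentrality with adjustment | Adjusted power | Net change (points) |
|---|---|---|---|
| 0 | 2.828 × 0.988 = 2.79 | 79.2% | −1.0 |
| 0.05 | 2.902 × 0.988 = 2.87 | 81.2% | +1.0 |
| 0.10 | 2.981 × 0.988 = 2.95 | 83.2% | +3.1 |
| 0.20 | 3.162 × 0.988 = 3.12 | 87.3% | +7.1 |

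**Step 4: break-even.** Adjustment pays once 1 − R² falls below 122/125 = 0.976, that is, R² above about 0.024. With ASA class as two indicator terms (k = 4), the limit is 1 − 121/125 = 0.032. Exact solution gives 0.024 and 0.032.

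**Step 5: does this survive the two-look design?** Two simulations at 64 per arm used four covariate terms, a slightly harsher charge. Each entry is adjusted against unadjusted power.

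| Assumed R² | 20,000 runs | 8,000 runs |
|---|---|---|
| 0 | 78.2% vs 79.4% | 77.9% vs 79.2% |
| 0.05 | 80.5% vs 79.9% | 81.1% vs 79.9% |
| 0.10 | 82.5% vs 79.2% | 82.7% vs 80.0% |
| 0.20 | 87.2% vs 79.8% | 86.6% vs 80.0% |

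Net changes are about −1, +1, +3 and +7 points, in line with step 3.

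**The case against.** The strongest reply is that nothing here is wrong. Under randomization the unadjusted test is valid. It matches the 48-hour SD used for sizing and delivers the stated power. That stands, and it makes this an improvement and not a correction.

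Four further points limit what can be claimed.

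- **Prognostic strength.** A reader might infer that adjustment is bound to raise power. The documents do not support this: they give no R² and do not call these variables prognostic, and below the break-even value the sign of the effect reverses. The BMI cap and the restriction to ASA 1-3 may also keep R² low.
- **Size.** A reader might treat 64 patients as worth 64/(1 − R²), or 67, 71 and 80 at the three R² values. That charges nothing for estimating the covariates and overstates the gain.
- **Availability.** A reader might infer that all three values are on file for every patient. The criteria require only threshold checks, and the data collection schedule (Appendix I) is not in the text available. Recording of a continuous defect area is therefore an inference.
- **Timing.** Defect area is measured during surgery, after randomization and the preoperative dose. The drug is unlikely to change it, so adjusting for it is reasonable, but it is not strictly a baseline value. A randomized patient who is not operated on would have none, which matters under intent to treat.

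The final level also deserves a note. Section 6.1 states a nominal 0.0219, whereas the spending function gives about 0.0237. At 0.0219 the unadjusted large-sample power is 79.4% and not 80.4%. The shift is about as large as the net gain at R² = 0.05, but it is a separate matter and does not bear on the choice between adjusted and unadjusted analysis.

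**Conclusion.** The point holds as a conditional one. The primary comparison is unadjusted, the three variables must be assessed anyway, and pre-specified adjustment could raise power at 64 per arm by about 1, 3 or 7 points if they explain 5%, 10% or 20% of the variance. It loses about 1 point if they explain nothing and breaks even at R² of about 0.02-0.03.

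These figures rest on assumed R² values, normally distributed outcomes on the hour scale, and the plan's 24-hour effect and 48-hour SD. If the primary outcome were analysed on another scale, they would need to be redone. The documents do not support reading this as an invalid analysis or an underpowered design. It is an inexpensive efficiency left unused, with a small and bounded downside.

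**What to change.** Before the interim look, amend section 6.3 as follows:

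1. Make the primary analysis a linear model (ANCOVA) of time to bowel function recovery on arm, BMI, ASA class as one ordinal term, and log defect area. Test the arm effect at the plan's one-sided levels at both looks.
2. Report the unadjusted t-test as supportive.
3. Confirm that the case report form captures defect area as a continuous value and not only as a check against 9 cm².
4. Replace a missing covariate by its pooled mean, computed blind to arm, so that every randomized patient stays in the intent-to-treat analysis.
5. Add a sensitivity model with BMI and ASA class only, because both are available before randomization.

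The cost is a wording amendment, plus one data field if continuous defect area is not already collected. No extra patients are needed. The statistical downside is up to about 1 point of power if the covariates prove uninformative.

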3.2 STUDY ENDPOINTS

3.2.1 PRIMARY ENDPOINT:

[Length of time \(hrs/days\) to gastrointestinal tract recovery](#)

3.2.1.1 PRIMARY ENDPOINT DEFINITION:

Time to gastrointestinal recovery will be measured by the following: Time to first flatus, time to toleration of a liquid diet, time to toleration of a solid diet, time to toleration or oral pain medications, time to first bowel movement, time to GI-2 recovery, time to GI-3 recovery, incidence of nasogastric tube insertion, episodes of emesis, use of anti-nausea medication, nausea, bloating, incidence of diet reduction or restriction, and initiation of TPN.

Time to first flatus and time to first bowel movement are patient reported endpoints that occur during the hospitalization. Patients will be asked about flatus twice daily by the physician or a qualified study or clinical staff member. Additionally, patients will be instructed to notify the nurse following first flatus and/or bowel movement so that the time can be recorded.

Toleration of a diet and toleration of oral pain medication are defined as ingestion of diet or medications that occurs without vomiting or significant nausea for four hours following ingestion.

GI-2 recovery is defined as both toleration of solid food and occurrence of first bowel movement. GI-3 recovery is defined as toleration of solid food and either occurrence of first flatus or occurrence of first bowel movement.

Patients requiring nasogastric tube insertion, requiring reduction or restriction of diet, having episodes of emesis, and/or needing initiation of TPN will be recorded. VAS

nausea, bloating and pain scores will be recorded by nursing staff at least twice each day. The number of doses of anti-nausea medication administered during the hospitalization will also be recorded.

3.2.2 *SECONDARY ENDPOINT(S):*

[Length of hospital stay](#), 30-day treatment related morbidity and re-admission rates, and post-operative pain scores.

3.2.2.1 *SECONDARY ENDPOINT DEFINITION(S):*

Length of stay will be measured in hours from the time that surgery is completed until the hospital discharge order is written (hrs/days).

Treatment related morbidity and re-admission rates will be assessed from the time surgery is completed to 30-days post-operatively. Treatment related morbidity and re-admission rates include: POI, indigestion, and any event determined by the attending physician to be directly related to treatment.

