5.3 PROCEDURES

Patients who meet all inclusion criteria will undergo the study related procedures stated below.

During enrollment, FH IDS will assign medication to patients in order of enrollment and according to the randomization code list. The patient will then receive medication dispensed from the bottle with the corresponding study ID.

Patient treatment will follow (section 5.1).

Following surgery, patients will be admitted to the hospital and a basic standardized treatment pathway will be initiated.

- 1) Following surgery patients are admitted with NPO status, PRN IV opioid pain medication, and PRN IV anti-nausea medication.
- 2) Epidural use is up to the discretions of the treating surgeon.
 - a. Non-narcotic adjuncts can be used as determined by the physician

- 3) Nasogastric tubes are NOT routinely left in following surgery. However, nasogastric tube use is up to the discretion of the treating surgeon. Patients who require NGT will be excluded from the study.
- 4) Patients remain NPO until the following criteria are met: reported flatus, absence of nausea and/or emesis and/or bloating, and absence of abdominal distention. Alternatively, clinical determination made by the physician can be utilized for diet advancement. If clinical determination outside of these parameters is used then the justification for the clinical decision making will be recorded for these patients.
- 5) Transition to oral pain medication will occur at or after the time of transition to clear liquids.
- 6) Diet advancement after clears will occur at physician discretion
- 7) Minimum discharge criteria include: toleration of diet beyond clears, toleration of oral pain medication, and absence of nausea/vomiting/distention.
 - a. Toleration of solid food is NOT required for discharge
 - b. Production of a bowel movement is NOT required for discharge

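### Section 6.3 expects no censoring, but section 5.3 lets patients go home before solid food or a bowel movement, and no rule covers a recovery time that is never observed

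*Combined protocol and SAP*

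**What the plan says.** Section 6.3 makes all efficacy analyses intention to treat and compares time to bowel function recovery and length of stay by Student's t-test. On incomplete times it says only: "Due to the short-term nature of the outcome measures we expect no censoring".

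Section 5.3, item 7, sets the discharge rule: "Minimum discharge criteria include: toleration of diet beyond clears, toleration of oral pain medication, and absence of nausea/vomiting/distention". Its sub-items add "Toleration of solid food is NOT required for discharge" and "Production of a bowel movement is NOT required for discharge".

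Section 3.2.1.1 lists first flatus, liquid diet, solid diet, oral pain medication, first bowel movement, GI-2 and GI-3 among the primary measures. It ties two of them to the inpatient stay: "Time to first flatus and time to first bowel movement are patient reported endpoints that occur during the hospitalization". GI-2 needs two events: "GI-2 recovery is defined as both toleration of solid food and occurrence of first bowel movement". GI-3 needs solid food plus either flatus or a bowel movement.

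Neither the sample size section (4.3.3) nor section 6.3 says which of these times is tested. The 2-week and 30-day contacts in section 3.2.2.1 are described for pain scores and the HerQLes survey only. The one carry-forward provision, in section 4.4.3, concerns unblinded subjects.

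**The concern.** A short-term outcome is not necessarily an observed one. What matters is whether the event comes before the patient leaves, and section 5.3 expressly allows it not to. For bowel movement, solid diet, GI-2 and GI-3, the t-test then has no value to use for such a patient.

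The loss is unlikely to be random. The study hypothesis (section 2) is that the drug shortens stay, so drug patients may leave unobserved more often. Two improvised remedies are open to the analyst:

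- **Dropping these patients** departs from intention to treat.
- **Using discharge time as the event time** turns the primary endpoint partly into length of stay, which is a separate secondary endpoint. It can show a recovery benefit where the drug only shortens stay.

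As written, the choice can be made with data in hand.

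**Working it through.** **1. Which times are exposed.**

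| Candidate time | Can discharge come first under 5.3? |
|---|---|
| Oral pain medication | No, it is a discharge criterion |
| Liquid diet | Normally no, diet beyond clears is required |
| First flatus | Less likely: "Patients remain NPO until the following criteria are met: reported flatus"; physician determination is the alternative route |
| Solid diet | Yes, item 7a |
| First bowel movement | Yes, item 7b |
| GI-2 | Yes, 7a and 7b |
| GI-3 | Yes, through its solid-food part, 7a |

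Length of stay ends at the discharge order, so no censoring is a fair expectation there.

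**2. The plan's own sample size.** Inputs from 4.3.3: difference 24 h, SD 48 h, one-sided 2.5%, 80% power. Fixed design: n = 2(1.960 + 0.842)² × 48²/24² = 62.8, so 63 per arm. With the third-degree power spending function at half information, 64 per arm gives 23.1% + 57.2% = 80.4% (before rounding), against the stated 22.9% + 57.1% = 80.0%. The arithmetic holds, but it counts every evaluable patient as having an observed time.

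**3. Power alone.** If 5, 10, 20, 30 or 40% of the 64 per arm have no time and are dropped, and the loss is unrelated to outcome, power is 78.3, 76.1, 71.1, 65.3 or 58.6%.

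**4. Bias, by illustration.** The documents give no rate of discharge before recovery, so these inputs are assumptions:

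- Event time E and discharge time D are correlated lognormals, SD 48 h each, correlation 0.3, 0.5 or 0.8.
- Placebo event mean is 96 h. Drug event mean is 96 h (no effect) or 72 h (24 h effect).
- Placebo discharge mean is 96 to 300 h (300 h = 12.5 days × 24). Drug discharge is 0, 12 or 24 h earlier.
- There is one look at one-sided 2.5% with 64 per arm.

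Assigning analyses min(E, D). Dropping analyses E only where E ≤ D. The rejection probability is Φ(δ/SE − 1.960), with δ the resulting mean difference and SE = √(s₀²/n₀ + s₁²/n₁).

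No true effect, discharge 12-24 h earlier on drug:

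| Placebo discharge mean | Unobserved, placebo | Unobserved, drug | False positive, assigning | False positive, dropping |
|---|---|---|---|---|
| 96 h | 50% | 61-84% | 17-71% | 0.3-4% |
| 120 h | 18-31% | 31-50% | 6-35% | 4-8% |
| 144 h | 5-17% | 10-31% | 3-14% | 5-10% |
| 168 h | 2-9% | 3-17% | 3-6% | 3-8% |
| 300 h | <1% | <1% | about 2.5% | about 3% |

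With equal discharge in both arms the rate is 2.4-2.6%. A finite-sample check with Student's t-test (20,000 trials) gave 17-71% for assigning at 96 h and 2.4-6.0% at 168 h.

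True 24 h effect, discharge 0-24 h earlier on drug:

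| Placebo discharge mean | Estimate, assigning | Estimate, dropping |
|---|---|---|
| 96 h | 14.2-23.5 h | 19.4-23.8 h |
| 120 h | 18.5-23.9 h | 19.3-24.1 h |
| 144 h | 21.2-24.2 h | 20.2-24.4 h |
| 168 h | 22.7-24.2 h | 21.5-24.6 h |
| 300 h | 24.0-24.1 h | 24.1-24.4 h |

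For assigning, the low ends arise when discharge does not move at all. When recovery and discharge both move by 24 h, both methods return about 23 to 25 h.

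A second illustration used independent gamma times, equal discharge in both arms and discharge means from 168 down to 96 h. The 24 h effect shrank to 21.7-13.6 h when assigning and 20.8-18.6 h when dropping.

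**The case against.** The strongest case against has four parts.

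- **The concern is conditional.** If the tested time is flatus or liquid diet, the usual pathway yields an observation before discharge. This stands, but the plan does not say so, and four listed times are exposed.
- **Collection may already be planned.** Appendix I, the data collection schedule named in section 6.1, is not in the available text. This stands as a limit. Even if it collects later times, section 6.3 would still need to name the endpoint and state a rule.
- **The only stay figure suggests little loss.** Section 1 cites a mean of 12.5 days, prolonged mostly by slow bowel recovery, and at that length the bias vanishes. But the reference title concerns complex abdominal wall defects, whereas this trial enrols elective single-staged repairs. Section 5.1 also foresees discharge before day 7. The figure does not settle the matter.
- **The large error rates need an unusual pattern.** They require no effect on recovery, clearly earlier discharge on drug in a double-blind trial, and stays about as short as recovery. This stands: 71% is an extreme, and under the study's joint hypothesis the estimate is nearly unbiased. It shows that the handling rule can matter, not that it will.

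Recruiting 70 to obtain 64 per arm (6/70 = 8.6% slack) absorbs some loss of power but does not address bias.

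**Conclusion.** The concern holds. The no-censoring expectation is contradicted by the plan's own discharge rule for bowel movement, solid diet, GI-2 and GI-3, and the available text has no rule for those patients. The effect ranges from negligible, when stays run well beyond recovery or discharge is equal in the arms, to serious, when stays are about as short as recovery and the drug brings discharge forward. Where in that range the trial falls cannot be derived from the documents, and every simulated figure rests on the assumed distributions and means. It should be fixed. Confidence is moderate, because the tested endpoint and Appendix I are both unknown.

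**What to change.** In section 6.3, replace the no-censoring sentence with text that does the following:

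1. Names the single recovery time that is tested.
2. For patients discharged before that event, records its date and time at the existing 2-week contact. If Appendix I already does this, only a cross-reference is needed.
3. Keeps every intention-to-treat patient in the analysis, and states that in the primary analysis discharge is neither counted as the event nor treated as non-informative censoring.
4. Keeps the comparison in hours, to match the 24 h / SD 48 h design: a mean difference or, if some times remain unobserved, a restricted-mean difference to a pre-specified horizon with censoring at last contact.
5. Pre-specifies a sensitivity analysis for unobserved and recalled times. Log-rank or Cox analyses can be supportive.

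The discharge rule is untouched. The cost is SAP wording plus one timed item (bowel movement or solid food) or two (GI-2 or GI-3) at a contact now described only for pain scores and HerQLes.

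The drawback is recall, especially for solid food, where toleration means eating "without vomiting or significant nausea for four hours following ingestion". In a check at correlation 0.5 with discharge 12-24 h earlier, mean-zero recall error of SD 12 h left power at 79-80%, and SD 24 h at 75-80%. The false-positive rate stayed at 2.3-2.7%. Zero mean is an assumption: a systematic error of b hours would shift the difference by b times the between-arm difference in recalled share, which the sensitivity analysis should cover. The 64 per group and the interim design need not change.
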